7.6.5 CT/MRA

Occurrence of severe PV stenosis: Severe PV stenosis is defined as a 70% or more reduction in PV diameter compared to the PV diameter measured at baseline. The number and percentage of subjects and number and percent of targeted PVs having severe PV stenosis at 3 months post-ablation as assessed by a central core lab will be summarized in the mITT analysis set.

7.6.6 Endoscopy

Occurrence of esophageal lesions: The number and percentage of subjects experiencing esophageal lesions as determined by post-procedure endoscopy assessed by a central core lab will be summarized in the mITT analysis set.

8 DATA MONITORING COMMITTEE

A Data Monitoring Committee (DMC) will assess subjects' data for safety on regular intervals for Wave I and Wave II and make recommendations on study adaptations as described in the DMC Charter. There will be no formal interim analysis (sample size analysis or early success analysis).

10.6.3 Simulation Results 30

10.7 Power and Type-I Error Simulations..... 33

List of Abbreviations

AAD	Antiarrhythmic Drug
AF	Atrial Fibrillation
AFEQT	Atrial Fibrillation Effect on Quality-of-life
AFL	Atrial Flutter
AT	Atrial Tachycardia
CEC	Clinical Events Committee
CSR	Clinical Study Report
CT	Computed Tomography
DMC	Data Monitoring Committee
ECG	ElectroCardioGram
FAS	Full Analysis Set
HRQoL	Health Related Quality of Life
ICF	Informed Consent Form
IRE	Irreversible Electroporation
mITT	Modified Intent-To-Treat
MMSE	Mini Mental State Examination
MRA	Magnetic Resonance Angiogram
MRI	Magnetic Resonance Imaging
mRS	Modified Rankin Scale
NIHSS	National Institutes of Health Stroke Scale
NSC	Non-study catheter
PAE	Primary Adverse Event
PAF	Paroxysmal Atrial Fibrillation
PFA	Pulsed Field ablation
PP	Per-Protocol
PV	Pulmonary Vein

PVI	Pulmonary Vein Isolation
QOL	Quality of Life
RF	Radiofrequency
SADE	Serious Adverse Device Effects
SAE	Serious Adverse Event
SAP	Statistical Analysis Plan

1 STUDY DESIGN

This clinical investigation is an interventional, prospective, single arm, multi-center, pre-market clinical evaluation of the IRE ablation system (Circular IRE Catheter and IRE Generator) to demonstrate safety and effectiveness when compared to predetermined performance goals. The study will enroll subjects with drug refractory, symptomatic paroxysmal atrial fibrillation (PAF) who are candidates for catheter ablation in two sequential waves. Wave I subjects will undergo the index procedure and additional neurological, pulmonary vein (PV), and esophageal assessments. Wave II will consist of roll-in and main study phase subjects. Subjects in Wave II will undergo the index procedure and same follow-up schedule as Wave I subjects, excluding the additional neurological, post-procedural PV (unless symptomatic), and esophageal assessments. This statistical analysis plan (SAP) describes the analyses that will be performed for roll-in and main phase subjects in Wave II. A separate SAP describes the analyses for subjects in Wave I.

To verify consistent workflow for study device components and to minimize the learning curve effect on the evaluation of safety and effectiveness of the IRE system, a maximum of 180 roll-in subjects (the first 1-3 subjects for each ablating physician) will be enrolled in the study. The size of the roll-in cohort may be smaller if enrollment in the main study phase terminates at the first sample size interim analysis. Operators who performed procedures in Wave I may be exempt from roll-ins for Wave II per training charter. Roll-in subjects will not be counted towards the enrollment cap of 330 main study subjects.

A Bayesian adaptive design will be used to determine sample size for Wave II. A maximum of 330 main study phase subjects is planned. The number of subjects at any individual site shall not exceed 20% of the total enrollment. All Wave II subjects will be evaluated at 7 days, 1, 3, 6 and 12 months following the index procedure. An additional interim analysis will be performed to claim early trial success.

2 TREATMENT ASSIGNMENT

All subjects will be treated with the IRE ablation system, whose components consist of

- Multi-channel IRE generator (D-1417-01-I)
- Multi-electrode circular IRE catheter (D-1412-01-SI)
- Related components and accessories

3 RANDOMIZATION AND BLINDING PROCEDURES

This is a non-randomized trial with all subjects receiving treatment with the IRE ablation system. Therefore, masking of treatment assignment for operators and subjects will not be performed.

This study will employ several measures to minimize operational bias:

- Screening logs will be maintained at sites to confirm consecutive eligible subjects are considered for participation in the study
- Timing of the interim analyses for sample size selection will not be revealed to sites
- An independent statistician will be responsible for performing interim analyses
- Results from the interim analyses will not be shared with the Sponsor or sites unless the interim analysis results in a decision to stop enrollment or to file for approval
- Sponsor personnel directly involved in the conduct of the study will not have access to intermediate aggregated summaries of primary safety and effectiveness endpoint data until preparation for filing for approval

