## 13. Study Medication

The following medications are applicable for this protocol:

- PRIOR to the procedure
  - Uninterrupted anticoagulation therapy should be in place at least 3 weeks prior to ablation procedure.
    - Recommendation: anticoagulation with warfarin (INR 2.0 to 3.0), a factor Xa inhibitor, or direct thrombin inhibitor is recommended for at least 3 weeks before and at least 4 weeks after ablation regardless of the CHA2DS2-VASc score or the method (electrical or pharmacological) used to restore sinus rhythm.
  - AAD therapy and administration of Proton Pump Inhibitors (PPI) should be managed as per the institution's standard of care
- DURING the procedure
  - Administer a heparin bolus prior to or immediately after transseptal puncture.
  - Optimally target an Activated Clotting Time (ACT) of 350-400 seconds prior to inserting the study catheter and throughout the procedure.
    - An ACT below 350 requires additional bolus of heparin until a minimal targeted ACT of 350 is reached.
    - It's strongly recommended to check ACT levels on regular basis during the procedure to ensure an ACT target of 350-400 seconds.
  - Flush all tubing and sheath continuously with heparinized saline.
- FOLLOWING the procedure
  - Anticoagulation therapy is strongly recommended for at least 2 months following ablation.
    - Decisions regarding continuation of systemic anticoagulation beyond 2 months post ablation should be based on the subject's stroke risk profile. Per HRS guidance systemic anticoagulation is recommended be continued beyond two months post-procedure in subjects with a CHA2DS2-VASc score of  $\geq 2$  (unless deemed contraindicated based on clinical considerations).
  - PPI administration following the procedure is MANDATORY if an endoscopy is performed post procedure.
  - AAD management during the study will be at the discretion of the investigator
  - Additional medications needed to treat clinical indications are at the discretion of the clinical investigation physician.

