#### 14.2.5 Repeat Ablation Procedures

Repeat procedures may be performed at the discretion of the investigator. It is highly recommended to collect arrhythmia documentation (in example documented recurrences) before performing a repeat procedure.

Repeat procedures during the blanking period (90 days post index procedure) must be conducted with the investigational device, with or without focal touch-up, if the arrhythmia is due to PV triggers. If the arrhythmia is due to non-PV triggers and the subject is treated with a commercially available ablation catheter and generator, the subject will be excluded from the long term effectiveness cohort.

Repeat procedures performed after the blanking period may be managed per investigator discretion using a commercially available ablation catheter and generator.

The follow-up schedule will remain based on the initial ablation procedure.

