6 SAMPLE SIZE JUSTIFICATION

A Bayesian adaptive design will be utilized to select the final sample size of the trial. Two sample size selection interim analyses will be performed based on the primary effectiveness endpoint. The first sample size selection interim analysis will be performed when enrollment in the mITT analysis set reaches 180. From simulations with realistic enrollment scenario, at this first interim timing, it is expected that about 30% of subjects will have between 3- and 6-months follow-up, about 18% of subjects will have between 6- and 9-months follow-up, and about 2% of subjects will have between 9- and 12-months follow-up. Predictive probabilities for trial success for the effectiveness endpoint will be used to determine whether the sample size of 180 will be sufficient or if the trial will continue enrollment. If the predictive probability with the current sample size of 180 is greater than 90%, or if the predictive probability with the maximum sample size of 330 is less than 2.5%, then enrollment will be stopped.

In case of continuation of enrollment, the second sample size interim analysis will be performed when enrollment in the mITT analysis set reaches 255. From simulations with realistic enrollment scenario, at this second interim timing, it is expected that about 27% of subjects will have between 3- and 6-months follow-up, about 27% of subjects will have between 6- and 9-months follow-up, and about 19% of subjects will have between 9- and 12-months follow-up. Predictive probabilities for trial success for the effectiveness endpoint will be used to determine whether the sample size of 255 will be sufficient or if the trial will continue to the full sample of 330. If the predictive probability with the current sample size of 255 is greater than 90%, or if the predictive probability with the maximum sample size of 330 is less than 2.5%, then enrollment will be stopped.

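### The Wave II SAP lets interim results go to the Sponsor or sites once a sample-size look stops enrolment, while most of the evaluation-period follow-up is still to be collected

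*SAP*

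**What the plan says.** Wave II SAP section 3 states that "masking of treatment assignment for operators and subjects will not be performed" and then lists measures to limit operational bias. Four matter here.

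- The timing of the sample-size looks is not revealed to sites.
- An independent statistician runs the interim analyses. SAP section 8 adds that the results are reviewed with the DMC.
- The release rule: "Results from the interim analyses will not be shared with the Sponsor or sites unless the interim analysis results in a decision to stop enrollment". The sentence goes on to add a decision to file for approval as a second exception.
- The bullet after it: "Sponsor personnel directly involved in the conduct of the study will not have access to intermediate aggregated summaries". This bar concerns the two primary endpoints and lasts until filing is being prepared.

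SAP section 6 places the sample-size looks at 180 and 255 mITT subjects. Enrolment stops if the predictive probability at the current size exceeds 90%, or if it is below 2.5% at 330. For the first look the SAP expects that "about 30% of subjects will have between 3- and 6-months follow-up, about 18% of subjects will have between 6- and 9-months follow-up". It puts a further 2% or so in the 9-12 month band.

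SAP section 7.4 puts the early-success test at the point where 30 subjects have 12 months of follow-up and all have 3 months. If that test fails, the final test uses full follow-up.

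On what sites control, Protocol section 13 says "AAD management during the study will be at the discretion of the investigator", and Protocol section 14.2.5 says "Repeat procedures may be performed at the discretion of the investigator".

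**The concern.** The filing exception is understandable, because a claim of success is then being made. The enrolment exception is different. When a sample-size look stops accrual, no hypothesis has been tested, and the tests that decide the trial rest largely on data the sites have yet to collect. The exception refers to results, not only to the decision, and it names the sites.

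The bullet that follows does not close the gap. It covers Sponsor personnel directly involved in conduct, not other Sponsor staff and not sites, and the SAP does not say which bullet prevails where they overlap.

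Knowing a favourable interim arrhythmia-free rate could alter how sites manage and monitor the remaining subjects. Two routes reach the primary endpoint.

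- **Drug use.** It is left to the investigator. The primary definition in SAP section 7.4.2 does not list a new or higher-dose antiarrhythmic drug as a failure; that criterion belongs to an additional endpoint in SAP section 7.6.3.
- **Monitoring effort.** At the final analysis, under SAP section 7.4.3, a failure-free subject with enough follow-up is missing on monitoring grounds only if all remote and Holter records are absent. Sparse monitoring can therefore count as success.

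**Working it through.** **1. How often the exception opens.** SAP Table 3.a, realistic enrolment, 65% effectiveness and 7% safety: enrolment stops at N=180 in 0.5535 of trials and at N=255 in 0.2854. The sum is 0.8389. The remaining 0.1611 go to N=330.

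**2. The SAP's own follow-up mix, reproduced.** I cumulated the realistic schedule in SAP Table 1 (7.5, 10.5, 13.5, 7.5, 15, 18, 24, then seven months at 30, then 24), with even accrual within each month. The 180th subject enters at month 9.8. The shares at 3-6, 6-9 and 9-12 months come out at about 30%, 18% and 3%, against the stated 30%, 18% and 2%. The first-look figures reproduce. The stated second-look figures (27%, 27%, 19%) do not: Table 1 gives about 34%, 18% and 12%. Both versions are carried below.

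**3. Evaluation follow-up outstanding.** The evaluation period is Day 91-365, or 9 months per subject. With band mid-points of 1.5, 4.5 and 7.5 months past blanking:

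- N=180: 0.30×1.5 + 0.18×4.5 + 0.02×7.5 = 1.41 months accrued. 1 − 1.41/9 = 84.3% outstanding.
- N=255: 0.27×1.5 + 0.27×4.5 + 0.19×7.5 = 3.045 months accrued. 1 − 3.045/9 = 66.2% outstanding.

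| Look | Stated shares, mid-points | All subjects at band ends | Table 1, realistic |
|---|---|---|---|
| N=180 | 84.3% | 76% to 93% | 84.5% |
| N=255 | 66.2% | 54% to 78% | 75.2% |

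At N=180 the slow and fast schedules give 80.0% and 83.8%. Half the subjects (1 − 0.30 − 0.18 − 0.02) have under 3 months of follow-up at that look, so they have no evaluation-period data.

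**4. Expected failures outstanding.** Person-time overstates what is open, because the hazard is front-loaded. SAP Table 2 at 65% gives weekly hazards of 0.1397, 0.0063 and 0.0037 over weeks 0-2, 2-8 and 8-39.

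- Full period: cumulative hazard 2×0.1397 + 6×0.0063 + 31×0.0037 = 0.4319. Failure probability 1 − exp(−0.4319) = 0.351.
- At the band mid-points (6.5, 19.5 and 32.5 weeks) the failure probabilities are 0.265, 0.302 and 0.335.
- N=180: (0.30×0.265 + 0.18×0.302 + 0.02×0.335)/0.351 = 40% already seen. With exact entry times from Table 1 it is 38%, so about 62% are still to come.
- N=255: the same sum with the stated shares gives 62% seen and 38% to come. Table 1 gives 51% seen and 49% to come.

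**5. What the early-success test uses after a stop at N=180.** On Table 1 the 30th subject enters at month 2.89, so the test falls at about month 14.9. By then 61.4% of evaluation follow-up has been collected, against 15.5% at the look. (61.4 − 15.5)/61.4 = 75% of the follow-up behind that test accrues after the look.

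**The case against.** The strongest reply is that results means only the decision. A stop has to be communicated, and on that reading the two bullets agree. The reading is possible, but the SAP does not state it. The DMC charter may restrict release further; it is not among the documents.

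Several other replies stand in whole or in part.

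- **Independent reading.** Protocol section 14.6 gives tracings and Holters to core laboratories or expert physicians. This narrows the monitoring route but does not close it: a reader sees only what was recorded, and Protocol section 14.3 says only that a core lab might be used for remote tracings.
- **Repeat ablation.** Under SAP section 7.4.2, a failure-free subject whose PVs are re-ablated with a commercial catheter in blanking leaves the primary analysis. A reader might infer that sites can remove subjects at will. Protocol section 14.2.5 does not support that: it requires the investigational device for PV-triggered repeats in blanking, so this route is limited.
- **Symptom contacts.** A reader might also count the sites' post-Holter calls. These verify symptoms, and the primary endpoint counts asymptomatic episodes too, so the calls bear on the symptomatic secondary endpoint.
- **The stop is itself informative.** Futility stops occur in at most 0.4% of simulated trials at 60-70% effectiveness (SAP Tables 3.c, 4.c and 5.c), so an early stop already signals a predictive probability above 90%. That cannot be avoided, but it is no reason to release counts and rates as well.

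**Conclusion.** The gap is real and should be closed. As written, section 3 permits interim results to reach unmasked sites and the Sponsor after a sample-size stop, which occurs in about 84% of simulated trials at the design assumptions. At N=180 (about 55% of trials) about 84% of evaluation follow-up and about 62% of expected failures are outstanding. At N=255 (about 29% of trials) it is about 66% of follow-up on the SAP's stated shares, or 75% from Table 1, and 38% to 49% of failures. The two figures near 84% measure different things, and the follow-up figure belongs to the first look only.

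These sizes rest on the SAP's realistic enrolment, its stated follow-up shares with mid-points, and its hazards at 65%. They measure exposure, not bias. A reader might infer that the effectiveness result will be distorted or the type I error inflated. The documents do not support that: they give no basis for estimating how far sites would change behaviour, and part of the signal comes from the stop itself. Nor can it be said that the Sponsor is unprotected, since its conduct staff are barred from aggregated summaries until filing is prepared.

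**What to change.** Amend the release bullet in Wave II SAP section 3 along these lines: after a sample-size selection look, only the decision to stop or continue enrolment is communicated to the Sponsor and sites; predictive probabilities, event counts and rates stay with the independent statistician and the DMC until the early-success criteria are met or the final analysis is done. This also settles the overlap with the bullet that follows. Put the same rule in the DMC charter.

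The cost is wording in two documents. No sample size, threshold, analysis or clinical procedure changes. The Sponsor loses early sight of numbers that it does not need in order to close enrolment. The change does not remove the signal carried by the stop itself.

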4 LEVELS OF SIGNIFICANCE

Significance levels for the interim and final analyses of the primary safety and effectiveness endpoints are described below in the relevant sections. The overall type-I error for the interim and final analyses of the primary safety and effectiveness endpoints are each controlled at a one-sided 2.5% level.

5 ANALYSIS SETS

5.1 Main Phase

For the analysis of study endpoints, the analysis sets defined in the following will be used:

- **Full Analysis Set (FAS):** The FAS will consist of all enrolled subjects who have had insertion of the study catheter (with or without delivery of pulse field ablation [PFA]).
- **Modified Intent-To-Treat (mITT) Analysis Set:** The mITT analysis set will consist of enrolled subjects who have had insertion of the study catheter and meet eligibility criteria.

- **Per Protocol (PP) Analysis Set:** The PP analysis set will consist of all enrolled subjects who satisfy the following criteria:
 - Have undergone ablation with the IRE ablation system.
 - Are treated for the study-related arrhythmia.
 - Are without major protocol deviations that would affect the scientific integrity of the primary safety and effectiveness data, including but not limited to the following:
 - Subjects found not meeting eligibility criteria
 - Use of the IRE ablation modality to ablate outside the PV region
 - Failure to check for entrance block for each targeted PV after adenosine/isoproterenol challenge

Eligible subjects treated with commercially available catheters for non-PV triggers that may arise during the index procedure or during repeat procedures occurring during the blanking period will be followed for the full duration of follow-up and will be evaluable for all endpoints in order to preclude potential bias that would arise from exclusion of these subject profiles from endpoint estimates.

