### 9.2 Participant Exclusion Criteria

Candidates will be excluded if ANY of the following criteria apply:

1. AF secondary to electrolyte imbalance, thyroid disease, or reversible or non-cardiac cause.
2. Previous LA ablation or surgery

3. Patients known to require ablation outside the PV region (e.g. CTI region, atrioventricular reentrant tachycardia, atrioventricular nodal reentry tachycardia, atrial tachycardia, ventricular tachycardia and Wolff-Parkinson-White).
4. Previously diagnosed with persistent AF (> 7 days in duration)
5. Severe dilatation of the LA (LAD >50mm antero-posterior diameter in case of Transthoracic Echocardiography (TTE))
6. Presence of LA thrombus
7. Severely compromised LVEF (LVEF <40%)
8. Uncontrolled heart failure or New York Heart Association (NYHA) Class III or IV
9. History of blood clotting, bleeding abnormalities or contraindication to anticoagulation (heparin, warfarin, or dabigatran)
10. History of a documented thromboembolic event (including TIA) within the past 6 months
11. Previous PCI/MI within the past 2 months
12. Coronary Artery Bypass Grafting (CABG) in conjunction with valvular surgery, cardiac surgery (e.g. ventriculotomy, atriotomy) or valvular cardiac (surgical or percutaneous) procedure.
13. Unstable angina pectoris within the past 6 months
14. Anticipated cardiac transplantation, cardiac surgery or other major surgery within the next 12 months.
15. Significant pulmonary disease (e.g., restrictive pulmonary disease, constrictive or chronic obstructive pulmonary disease) or any other disease or malfunction of the lungs or respiratory system that produces severe chronic symptoms
16. Known significant PV anomaly that in the opinion of the investigator would preclude enrollment in this study
17. Has known pulmonary vein stenosis
18. Acute illness, active systemic infection or sepsis
19. Presence of intracardiac thrombus, myxoma, tumor, interatrial baffle or patch or other abnormality that precludes catheter introduction or manipulation.
20. Severe mitral regurgitation
21. Presence of implanted pacemaker or Implantable Cardioverter-Defibrillator (ICD) or other implanted metal cardiac device that may interfere with the IRE energy field.
22. Presence of a condition that precludes vascular access (such as IVC filter)
23. Significant congenital anomaly or a medical problem that in the opinion of the investigator would preclude enrollment in this study

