7.4.2 Long-Term Effectiveness

The primary effectiveness endpoint is defined as freedom from documented (symptomatic and asymptomatic) atrial arrhythmia (atrial fibrillation [AF], atrial tachycardia [AT] or atrial flutter [AFL]) recurrence based on electrocardiographic data (≥ 30 seconds on arrhythmia monitoring device) during the effectiveness evaluation period (Day 91-Day 365). Acute procedural failure (i.e., failure to confirm entrance block in all PVs except those that are silent and/or cannot be cannulated post-procedure, use of a non-study catheter for PV isolation, or failure to have PFA delivery with the study catheter due to IRE system malfunctions) will also be considered a long-term effectiveness failure. Subjects without effectiveness failure who undergo a repeat ablation procedure during the blanking period where PVs were ablated with a commercially available catheter and generator will be considered non-assessable for long-term effectiveness of the IRE ablation system and thus will be excluded from this analysis.

The primary effectiveness endpoint will be summarized descriptively in the PP analysis set. The number and percentage of subjects free from primary effectiveness failure during the evaluation period will be presented.

The following additional analyses will be performed at the time of the effectiveness analysis:

- **Sensitivity to Analysis Set**

The primary effectiveness endpoint will be analyzed in the mITT and FAS analysis sets as sensitivity analyses.

- **Kaplan-Meier Analysis**

Kaplan-Meier estimates and plots will be used to characterize the time to the first primary effectiveness event, including acute procedural failure and documented symptomatic/asymptomatic AF, AT, or AFL recurrence following the initial ablation

procedure, in the FAS, mITT, and PP analysis sets. The probability of freedom from primary effectiveness failure at each follow-up timepoint post blanking will be presented.

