7.4.1 Primary Safety Endpoint

The primary safety endpoint is the occurrence of any PAE within 7 days of the initial mapping and ablation procedure. The definition of PAE can be found in section 8.2.1 of the study protocol.

The PAE rate will be compared against a performance goal of 14% by testing the following hypotheses:

$$H_0: p_s \geq 0.14 \quad vs \quad H_A: p_s < 0.14,$$

Where p_s is the PAE rate. The mITT analysis set will be the primary analysis set for the early success interim analysis and final analysis of primary safety endpoint.

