7.4.1.1 Early Success Interim Analysis of Primary Safety Endpoint

The primary safety outcome for all subjects will be known at the time of the interim analysis and will be used for hypothesis testing. Notably, primary adverse events only occur within a 3-month window of the procedure by definition (with the exception of a procedure or device related death, pulmonary vein stenosis, and atrio-esophageal fistula) which will result in nearly identical hypothesis tests at the interim and final analyses.

At the time of the early success interim analysis, the primary safety endpoint will be met if:

$$\Pr(p_s < 0.14 | y, n) > 0.975$$

where p_s is the PAE rate. A beta-binomial model with a non-informative uniform prior Beta (1,1) will be used for the safety rate. If the posterior probability of the safety rate being less than 14% is greater than 0.975 then the study will be considered to have demonstrated safety of the device at the early success interim analysis.

To investigate the robustness of the analysis result, the following sensitivity analyses will be performed in the FAS and mITT analysis sets unless otherwise noted at the time of the early success interim analysis with available data:

- **Sensitivity to Analysis Set**

The primary safety endpoint will be analyzed in the FAS as a sensitivity analysis.

- **Snap-Shot Binomial Analysis**

The number and percentage of subjects with primary safety events will be presented along with one-sided 97.5% exact binomial upper confidence bounds. Subjects with missing outcomes will be excluded from the analysis. Missing outcomes of primary safety endpoints is defined in Section 7.4.3.

- **Best-case Scenario**

The point estimate for the PAE rate will be estimated by treating subjects with missing primary safety outcomes as free from primary safety events.

- **Worst-case Scenario**

The point estimate for the PAE rate will be estimated by treating subjects with missing primary safety outcomes as failures.

- **Tipping Point Analysis**

Tipping point analysis will be performed for the primary safety endpoint to assess the impact of missing outcomes on the safety conclusion. The posterior distribution will be updated each time treating a subject with a missing outcome as failure to evaluate whether a tipping point is identified.

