7.4.2.2 Final Analysis of Primary Effectiveness Endpoint

If trial success is not declared at the early success interim, the final analysis for the primary effectiveness endpoint will use a beta-binomial model with a non-informative uniform prior Beta (1,1) based on complete 12-month follow-up data. At the time of the final analysis, the primary effectiveness endpoint will be considered as success if:

$$\Pr(p_E > 0.50|x, n) > 0.9775$$

where p_E is the 12-month effectiveness success rate. If the posterior probability of the effectiveness rate being greater than 50% is greater than 0.9775 then the study will be considered to have demonstrated effectiveness of the device.

To investigate the robustness of the analysis result, the following sensitivity analyses will be performed in the mITT and PP analysis sets unless otherwise noted at the time of the final effectiveness analysis:

- **Sensitivity to Analysis Set**

The primary effectiveness endpoint will be analyzed in the mITT analysis set as a sensitivity analysis.

- **Snap-Shot Binomial Analysis**

Number and percentage of subjects free from primary effectiveness failure will be presented along with one-sided 97.75% exact binomial lower confidence bounds. Subjects with missing outcomes will be excluded from this analysis. Missing outcomes of primary effectiveness endpoints is defined in Section 7.4.3.

- **Kaplan-Meier Analysis**

Kaplan-Meier estimates and plots will be used to characterize the time to first primary effectiveness event, including acute procedural failure and documented symptomatic/asymptomatic AF, AT, or AFL recurrence following the initial ablation procedure. This will provide a non-parametric estimate of the primary effectiveness endpoint. The Kaplan-Meier analysis will account for all follow-up time for all subjects in the analysis set. Subjects with incomplete follow-up who remain failure free will be censored at the time of last observation. The probability of freedom from primary effectiveness failure at each monthly timepoint post blanking will be presented along with the one-sided 97.75% lower confidence bound using Greenwood's variance.

- **Best-case Scenario**

The point estimate for freedom from primary effectiveness failure will be estimated by treating subjects with missing primary effectiveness outcomes as free from primary effectiveness events.

- **Worst-case Scenario**

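### Wave II: the deciding analyses drop treated subjects judged ineligible, with no rule tying that judgement to pre-insertion information or blinding it to outcome, so the 2.5% error level is not assured

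*SAP*

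**What the plan says.** **Safety.** Wave II SAP 5.1 defines mITT as "enrolled subjects who have had insertion of the study catheter and meet eligibility criteria"; protocol 20.3.2 does the same. SAP 7.4.1 states: "The mITT analysis set will be the primary analysis set for the early success interim analysis and final analysis of primary safety endpoint". Protocol 20.4.4 and 20.4.4.3 also name mITT for safety. FAS, which needs only catheter insertion, is secondary. SAP 7.4.1.1 says "The primary safety endpoint will be analyzed in the FAS as a sensitivity analysis", and 7.4.1.2 repeats this for the final analysis.

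**Effectiveness.** SAP 7.4.2 makes PP the primary set, and SAP 5.1 counts failure to meet eligibility among the major deviations that remove a subject from PP. The alternative set in SAP 7.4.2.1 and 7.4.2.2 is mITT: "The primary effectiveness endpoint will be analyzed in the mITT analysis set as a sensitivity analysis". The Wave I SAP goes further: "The primary effectiveness endpoint will be analyzed in the mITT and FAS analysis sets as sensitivity analyses". For the additional effectiveness endpoints, protocol 20.4.6 plans FAS and PP, but Wave II SAP 7.6.3 uses mITT and PP.

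**When eligibility is settled.** Protocol 10.2 and 10.3 deal with ineligibility found before insertion; those subjects never enter FAS. For a subject already treated, neither document gives a cut-off date, a data source, a decision-maker or a blinding rule. The Clinical Events Committee adjudicates PAEs (protocol 6.4.2), and the bias measures in SAP 3 do not mention eligibility.

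**Error level.** SAP 4 says the type I errors for safety and effectiveness "are each controlled at a one-sided 2.5% level".

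**The concern.** Subjects found ineligible before insertion are already out, so the eligibility filter in mITT and PP can act only on subjects who had the catheter inserted. The trial is unmasked, and PAEs reach the sponsor within 72 hours (protocol Table 11), so the outcome may well be known when eligibility is judged.

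Some criteria leave room for judgement. Exclusion 23 partly rests on investigator opinion. Exclusion 1, "AF secondary to electrolyte imbalance, thyroid disease, or reversible or non-cardiac cause", has no matching baseline laboratory test in the visit schedule, so work-up of a recurrence could bring it to light. The second example bears on effectiveness, not on the safety test.

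If an event makes it more likely that a subject is found ineligible, removal lowers the PAE rate and raises the success rate that are compared with fixed goals. There is no control arm in which the same process would offset it. A patient exposed to the device would also drop out of the analysis that decides the safety claim.

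**Working it through.** **Inputs.** Goal 14%, prior Beta(1,1) and the 0.975 threshold: "If the posterior probability of the safety rate being less than 14% is greater than 0.975" (SAP 7.4.1.1). N = 180, 255, 330 (SAP 6). Safety drop-out is 5% per year (Appendix 10.6.2). Event-free subjects with under 3 months of follow-up are excluded (SAP 7.4.3), so drop-out by 3 months is d = 1 − 0.95^(1/4) = 1.27%.

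**Decision rule.** Let c(n) be the largest y with Pr(p < 0.14 | Beta(1+y, 1+n−y)) > 0.975. Then c = 16, 24 and 33 at n = 180, 255 and 330.

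**The plan's own figures first.** Pass probability at N = Σ over n of Bin(n; N, 1−d) × P(Y ≤ c(n) | n, p).

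- Power at p = 7% is 0.8249, 0.9487, 0.9854. Weighted by the Table 3.a sample-size proportions for 65% effectiveness: 0.5535×0.8249 + 0.2854×0.9487 + 0.1611×0.9854 = 0.886. The SAP gives 0.8853.
- Type I error at p = 14% is 1.79%, 2.11%, 2.19%. Table 3.b gives 1.72% (1.56% to 1.89%). Its scenario assumes near-perfect effectiveness, so enrolment should almost always stop at 180; 1.79% lies in the interval.

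**Adding removal.** Suppose a fraction a of PAE subjects and b of other subjects are later ruled ineligible. The rate in mITT becomes p′ = 0.14(1−a) / [0.14(1−a) + 0.86(1−b)]. For a = 5%, b = 1%: 0.133 / (0.133 + 0.8514) = 13.51%. The documents give no values for a and b; all are assumptions.

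| a / b | p′ | N=180 | N=255 | N=330 |
|---|---|---|---|---|
| none, or equal 3% / 3% | 14.00% | 1.79% | 2.11% | 2.19% |
| 2% / 1% | 13.88% | 1.99% | 2.39% | 2.53% |
| 4% / 2% | 13.75% | 2.22% | 2.72% | 2.92% |
| 5% / 1% | 13.51% | 2.74% | 3.46% | 3.84% |
| 10% / 2% | 13.01% | 4.16% | 5.59% | 6.56% |

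Here N is the mITT size after removals. If removals instead shrink a treated group of N and nobody drops out, 5% / 1% gives 2.76%, 3.50%, 3.82% and 10% / 2% gives 4.63%, 5.35%, 6.32%.

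**In single subjects.** If exactly k PAE subjects are removed from n+k treated, the error is P(Y ≤ c(n)+k | n+k, 0.14), averaged over n as above. For k = 1 it is 2.98%, 3.17%, 3.12%; for k = 2 it is 4.72%, 4.62%, 4.33%.

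**Effectiveness.** Take fixed n = 153, 217, 281 (15% drop-out), a true rate of 50% and threshold 0.9775; at least 89, 124 and 158 successes are then needed. The error is 2.6%, 2.1%, 2.1% with no removal. If 5% of failures and no successes are removed, p′ = 0.5 / (0.5 + 0.475) = 51.28% and the error is 5.2%, 4.8%, 5.5%. These are fixed-n figures, not those of the adaptive design, for which Table 3.b gives 1.68%.

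**What the simulations cover.** Appendix I simulates failures, PAEs, drop-out and enrolment. It has no step that removes subjects for ineligibility after treatment.

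**The case against.** The strongest reply is that this is an inference from silence. A reader might infer that the plan allows eligibility to be reopened after an event, and that the 2.5% level is therefore broken. The documents support neither. They state no such rule, and the error rises above 2.5% only if removal depends on outcome to a sufficient degree. Equal removal does no harm, and 2% against 1% stays at about 2.5%.

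Nor can it be said that event-free subjects are never re-examined. Protocol 19, 22 and 24.1.1 provide for source verification and for records sufficient to verify selection criteria, whatever the outcome, and protocol 17 prohibits waivers. Some possible triggers are also weak. Thrombus imaging is mandatory the day before or the day of ablation (protocol 14.2.1), and exclusions 4 and 9 are worded largely around prior diagnosis or history.

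The safety sensitivity analyses run in FAS at both looks, and SAP 7.6.2 reports individual PAEs in FAS, so a removed PAE would be visible. If ineligible subjects simply carry more risk and are found regardless of outcome, mITT validly estimates the rate in eligible patients.

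All of this stands, and it limits the claim. It does not supply the missing rule. Routine verification does not rule out closer scrutiny of event cases, and the FAS safety result does not decide success. For Wave II effectiveness the only alternative set carries the same eligibility filter.

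**Conclusion.** The concern holds as a gap in protection, not as a demonstrated error. The plan does not prevent outcome-dependent removal from the sets that decide Wave II, and its type I error simulations do not cover it, so control at 2.5% is not assured. The size rests wholly on assumed removal rates: about 2.7% to 3.8% for 5% against 1%, about 4.2% to 6.6% for 10% against 2%, and about 2.5% or less for 2% against 1% or equal removal. The margin is thin, since one PAE subject removed because of the event takes the safety error to about 3%. Effectiveness is less protected than safety, because no Wave II main-phase effectiveness analysis in the SAP uses FAS, although the Wave I SAP does and protocol 20.4.6 planned it for the additional effectiveness endpoints.

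**What to change.** 1. Make FAS the primary set for the safety test at the early success and final analyses, with mITT as sensitivity. Change SAP 7.4.1 and amend protocol 20.4.4 and 20.4.4.3; a change to the SAP alone would contradict the protocol.
2. State in SAP 5.1 that eligibility for mITT and PP is judged only on information dated before catheter insertion, and that the decision is fixed before endpoint data are reviewed.
3. Add FAS to the Wave II effectiveness sensitivity analyses in SAP 7.4.2.1 and 7.4.2.2, as in the Wave I SAP, and reconcile SAP 7.6.3 with protocol 20.4.6.

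With all treated subjects in the safety test, the calculation above returns 1.79%, 2.11% and 2.19%. The cost is a short protocol and SAP amendment and a little more analysis in a set that is already defined. The PAE rate may be slightly less favourable, because treated subjects found ineligible would count.
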